### 7.2 Secondary Endpoints

To assess the long-term efficacy of Chronocort®, the following secondary endpoints will be assessed:

- 1. Total daily dose of Chronocort® in mg/day of hydrocortisone and by BSA
- 2. Disease control throughout the study as assessed by both 17-OHP and A4 levels in the optimal and normal range, respectively, at 09:00 and at 13:00, and by the proportion of dose given at night
- 3. Change from pre-Chronocort® baseline at each visit in SDS of 17-OHP and A4 at 09:00, 13:00 and the mean of the two timepoints. Pre-Chronocort® baseline means prior to the first dose of continuous Chronocort® which is:
  - O The reassessed baseline under DIUR-006 for subjects entering from study DIUR-003 and those subjects from DIUR-005 who had a gap between completing study DIUR-005 and starting study DIUR-006,
  - Visit 4 (Week 24) from the feeder study for subjects who received standard glucocorticoid replacement therapy in study DIUR-005 and immediately entered DIUR-006,
  - o Prior to the first Chronocort® dose in study DIUR-005 for subjects who received Chronocort® in study DIUR-005 (i.e. DIUR-005 baseline visit) and immediately entered DIUR-006.
- 4. Change from pre-Chronocort® baseline at each visit in the absolute values of 17-OHP and A4 at 09:00 and 13:00
- 5. Change from pre-Chronocort® baseline at each visit in:
  - a. Bone turnover markers CTX, osteocalcin
  - b. Testosterone (total)
  - c. Fasting insulin and blood glucose levels, and HbA1c
  - d. hsCRP and PRA

Version: 20.0 – 16 Jun 2022 Page **22** of **96** 

- e. Body composition (DEXA)(fat mass, lean mass and total bone density) (except in Germany)
- f. Quality of life SF-36®, MAF, EQ-5DTM
- 6. Incidence of dose titrations

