#### **13.6.2** Efficacy

The total daily dose of Chronocort® in mg/day of hydrocortisone and by BSA will be summarised over time.

Disease control will be based on whether 17-OHP levels are in the optimal range and also whether the A4 levels are in the normal range (both analysed separately). A subject will be considered a responder (i.e. disease controlled) if their 09:00 results are in the optimal range for 17-OHP and then separately if their 09:00 results for A4 are in the normal range. The number and percentage of subjects achieving results in the optimal range will be presented at each visit and by the proportion of dose given at night. This will be repeated for the 13:00 values.

DEXA scans will be performed at baseline for subjects entering from study DIUR-003 and then annually for all subjects, except in Germany. Summary statistics will be produced for the absolute values and change from pre-Chronocort® baseline for fat mass, lean mass, total bone density, T scores and Z scores at each visit. Due to the length of the study, it is possible that there will be changes in the DEXA scanners used at some sites. Therefore, the above summary tables will be repeated excluding data collected after a scanner change and an analysis of variance (ANOVA) model will be created to explore whether there is any statistically significant difference in the DEXA results before and any scanner changes.

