13.4. DEXA scans

Body composition (DEXA) scans will be performed at baseline for subjects entering from study DIUR-003 and then annually for all subjects, except in Germany. Summary statistics will be produced for the absolute values and change from pre-Chronocort® baseline (see Section 9.3.2) for each of fat mass, lean mass, total bone density, T scores and Z scores at each visit.

Due to the length of the study it is possibly that there will be changes in DEXA scanner at some sites. Therefore, the above summary tables will be repeated excluding data post scanner change.

In addition, to explore the potential impact of changes in scanner, an ANOVA 'Analysis of Variance' model will be created to explore whether there is any statistically significant difference in the DEXA results before and after this scanner change. The ANOVA will look at the DEXA scan results (T score and Z score separately and exclusively) at two timepoints: firstly, at the last timepoint for each subject prior to the change in scanner; and secondly at the first DEXA scan for each subject post-scanner change. The response variable in the ANOVA will be the change in the DEXA scan between these two timepoints (ie. the calculated 'post-scanner-result' minus 'pre-scanner-result' for each patient). The ANOVA will use the population of scan result origin as the categorical factor in the analysis: the first level of the population factor will be for 'All subjects' (ie. the Full <Interim> analysis set excluding those subjects with a change in scanner) and the second level of the population factor will be only those Full <Interim> Analysis set subjects who have been exposed to the new DEXA scanner. Using the ANOVA results, the effect size for the difference in mean change between the two populations will be calculated, along with a measure of its statistical significance. These results will be presented in a separate table: 'Change in DEXA scanner results by site population'.

Version: 6.0 12 July 2022

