If the difference in mean change between populations is found to be statistically significant at the 5% level, then a second version of the DEXA summary table 'Summary of absolute values of body composition — Dual Energy X-ray Absorptiometry (Full <Interim> analysis set)' will be created exclusively for those parameters, with the subjects' measurements following the scanner change adjusted upwards or downwards by the difference in mean changes between the 'Scanner change' population and the 'All subjects' population from the ANOVA.

In the event of multiple sites changing their DEXA scanners, a separate ANOVA model will be created for each site. Each resulting ANOVA model will continue to compare the 'All subjects' reference results against the site under analysis, but the 'All subjects' set will exclude any data collected from other sites at which the DEXA scanner is changed during the interval between the two timepoints under consideration in the given ANOVA model (ie. the 'All subjects' reference collection used in each ANOVA must compute each patient's change in DEXA scan results between the two timepoints using the same DEXA scanner).

A detailed listing of all DEXA scan results will be produced and will include the date of scanner change and a normal reference flag as described in Section 9.2.4.

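### The scanner-shift analysis in SAP 13.4 covers only T and Z scores, and its adjusted table depends on p<0.05 and omits change from baseline

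*SAP*

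**What the plan says.** Protocol 7.2 names the endpoint as change from pre-Chronocort baseline in "Body composition (DEXA)(fat mass, lean mass and total bone density". SAP 2.2.2 adds T score and Z score, making five parameters. Protocol 13.6.2 says that an "analysis of variance (ANOVA) model will be created to explore whether there is any statistically significant difference in the DEXA results" around any scanner change. It does not restrict the parameters and has no correction step.

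SAP 13.4 narrows and extends this:

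- **Parameters.** "The ANOVA will look at the DEXA scan results (T score and Z score separately and exclusively) at two timepoints": the last scan before the change and the first after it. The reference group is subjects with no scanner change.
- **Trigger.** An adjustment follows only "If the difference in mean change between populations is found to be statistically significant at the 5% level".
- **Output.** In that case "then a second version of the DEXA summary table 'Summary of absolute values of body composition" is produced. It "will be created exclusively for those parameters, with the subjects' measurements following the scanner change adjusted upwards or downwards" by the estimated difference in mean change. The text mentions no adjusted change-from-baseline table, and SAP 16.1 lists no adjusted DEXA table of either kind.
- **Unit.** "In the event of multiple sites changing their DEXA scanners, a separate ANOVA model will be created for each site".

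Two provisions do not depend on the test. The absolute and change summaries for all five parameters are repeated without post-change scans (Tables 14.2.4.1.2 and 14.2.4.2.2). The T and Z effect size and its significance are tabulated whatever the p-value (Table 14.2.4.3). No confidence interval is specified for that effect size.

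**The concern.** A step change from a new scanner enters every later within-subject change at that site. It can look like, or hide, a drift in body composition over a follow-up of up to 5.5 years. Three features of the plan deal with this poorly.

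1. Fat mass, lean mass and total bone density get no estimate of the shift, so a reader of their tables cannot judge how much of a late trend might come from the scanner.
2. The adjustment goes to absolute values, although the endpoint is change from baseline. Table 14.2.4.2.1 mixes scanners and has no adjusted counterpart.
3. A p-value decides whether an adjusted table appears, in a study with no sample-size basis (Protocol 13.7). Low power means a real shift may prompt no adjusted table. When the test does fire, the estimate that passed the threshold is also the correction applied, so on average it is too far from zero.

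**Working it through.** The plan states no power, effect size or site count for this test, so there is no figure to reproduce. What follows is illustrative.

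**Inputs from the documents.** The trigger is p<0.05 (SAP 13.4). The study has at most 138 subjects (Protocol 13.7). Germany does no DEXA. The only site size given is 16, the single DIUR-003 centre (Protocol 5.5).

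**Assumed inputs.** 3 to 16 subjects at the changed site (n), 80 reference subjects (m; 40 and 110 also tried), and a true shift d in units of the SD of the between-scan change.

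**Step 1: what the trigger demands.** A two-group ANOVA equals a two-sided t test. The standard error of the estimated shift, in SD units, is √(1/n + 1/m). The smallest observed difference reaching p<0.05 is t(0.975, n+m−2) times that. For n = 8, m = 80: √(1/8 + 1/80) = 0.371, and 1.988 × 0.371 = 0.74 SD. For n = 5 it is 0.92 and for n = 16 it is 0.54.

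**Step 2: how often it fires, and with what estimate.** Power comes from the noncentral t with noncentrality d/√(1/n + 1/m). The mean estimate given significance comes from simulation (200,000 draws).

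| n at site | d | Test fires | Mean estimate when it fires | Excess over d |
|---|---|---|---|---|
| 5 | 0.5 | 19% | 1.14 | 0.64 |
| 8 | 0.5 | 27% | 0.95 | 0.45 |
| 16 | 0.5 | 44% | 0.74 | 0.24 |
| 5 | 0.75 | 36% | 1.22 | 0.47 |
| 8 | 0.75 | 52% | 1.03 | 0.28 |
| 16 | 0.75 | 77% | 0.86 | 0.11 |

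At d = 0.5, the range from n = 3 to n = 16 is 13% to 38% with 40 reference subjects and 14% to 46% with 110, so the reference size matters little. For d = 1.0 with 80 reference subjects, the test fires 39% of the time at n = 3 and 95% at n = 16. The shift needed for 80% power is 1.31 SD (n = 5), 1.05 (n = 8) and 0.78 (n = 16).

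**Step 3: false triggers.** With no real shift and k tests, the chance of at least one trigger is 1 − 0.95^k. The lower figure treats T and Z as fully correlated (k = number of sites), the upper as independent (k = 2 × sites). One site gives 5–10%, three sites 14–26%, and five sites 23–40%.

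**Step 4: effect on the overall mean, one changed site.** An unadjusted shift moves the mean of n + m subjects by d × n/(n + m). For d = 0.5 this is 0.5 × 5/85 = 0.03, 0.5 × 8/88 = 0.05 and 0.5 × 16/96 = 0.08 SD. The excess correction moves it by 0.64 × 5/85, 0.45 × 8/88 and 0.24 × 16/96, about 0.04 SD each. The effect is small overall but larger in a narrow column. The protocol synopsis summarises efficacy by study and all DIUR-003 subjects came from one site, so a scanner change there would put the full shift d into the DIUR-003 column after the change.

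**The case against.** The strongest objection is that the plan already protects the endpoint. The exclusion tables cover absolute values and change for all five parameters, unconditionally. A reader might infer from the missing adjusted change table that scanner effects on the change endpoints are ignored. Table 14.2.4.2.2 shows otherwise.

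A reader might also infer that non-significance is treated as proof of no shift. The SAP does not say so. The threshold controls only an additional table. The unadjusted and exclusion tables stay, and the T and Z effect size is shown either way. Any over-correction is confined to that additional table.

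A third tempting reading is that narrowing the ANOVA to T and Z scores is an undeclared departure from the protocol. That is too strong. The protocol calls the ANOVA exploratory, Protocol 13 lets minor method changes be documented in the SAP, and the SAP revision history for version 6.0 records the restriction.

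The figures also rest on assumed inputs, and site size and shift size matter most. With a 1.0 SD shift and 16 subjects the test rarely misses. Finally, adjusting regardless of significance has a price: at n = 5 the shift estimate has a standard error of √(1/5 + 1/80) = 0.46 SD, so the adjusted values can be noisier than the unadjusted ones when the true shift is small.

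All of this stands and limits the consequence. It does not explain why the three protocol-named parameters get no shift estimate, why the estimate that is planned has no interval, or why the adjusted output omits the endpoint's own scale.

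**Conclusion.** The gap is real but modest. SAP 13.4 estimates a scanner shift for two of five parameters and reserves adjustment for significant results and absolute values. Under the assumptions above, a 0.5 SD shift at a site of 5 to 16 subjects triggers the adjustment 19% to 44% of the time, and the correction then averages 1.5 to 2.3 times the true shift (0.74/0.5 and 1.14/0.5). The direction of that bias, away from zero, follows from selecting on significance. Its size depends on inputs the documents do not give, and small sites are an inference from the study total. Separate per-site models are explicit only if several sites change scanner.

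The documents do not support the claim that the long-term body-composition results are left exposed, because scanner-clean change tables are planned in every case and the endpoint is secondary and descriptive. This is a cheap improvement.

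**What to change.** In SAP 13.4:

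- Run the scanner comparison for all five DEXA parameters, in line with Protocol 13.6.2, and report each estimated shift with a 95% CI whatever the p-value.
- Remove the 5% trigger. If an adjusted table is shown, present it as a sensitivity analysis for all five parameters, for change from baseline as well as absolute values, regardless of significance and alongside the unadjusted and exclusion tables. Add it to the list in SAP 16.1.

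Making the exclusion tables the main DEXA result is a possible further step but a trade-off, since it drops late scans in a long-term study. It is not needed here.

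The cost is revised SAP wording, the same model for three more parameters and a few more tables. Where a site has few subjects the adjustment will be noisy. The interval makes that visible: its half-width in Step 1 is about 0.92 SD at n = 5.

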13.5. Quality of life questionnaires

Quality of life will be assessed at baseline, week 24 and 6-monthly thereafter, measured using three instruments: SF-36°, MAF, EQ-5D™.

SF-36®

The SF-36v2 questionnaire is a multipurpose, generic, short-form health survey containing 36 questions (4-week recall) yielding 8 health domain scales and 2 psychometrically based physical and mental component summary measures (Maruish 2011).

The 8 health domain scales are referred to as:

- 'Physical Functioning',
- 'Role- Physical',
- 'Bodily Pain',
- 'General Health',
- 'Vitality',
- 'Social Functioning',
- 'Role-Emotional',
- and 'Mental Health'.

The 2 summary measures are referred to as the physical component score and mental component score

Standardised scores will be generated using the validated scoring software package (QualityMetric Health Outcomes™ Scoring Software 4.5) for the 8 health domain scales and 2 summary measures using the raw data entered in the eCRFs.

For each summary measure and scale, the change from baseline and percentage change from baseline at each visit will be calculated. Summary statistics for absolute values at each visit, change

Version: 6.0 12 July 2022

and percentage change from baseline will be tabulated by previous treatment group, visit, feeder study and overall DIUR-006 study.

Individual question scores, summary measure scores and scale scores will be listed.

Multidimensional Assessment of Fatigue

The MAF is a self-administered questionnaire consisting of 16 questions. The Global Fatigue Index (GFI) will be calculated using a standard method specific to the MAF questionnaire. This combines the responses to the questionnaire to give one score ranging from 1 (no fatigue) to 50 (severe fatigue).

To calculate the GFI: Convert item #15 to a 0-10 scale by multiplying each score by 2.5 and then sum items #1, 2, 3, average #4-14, and newly scored item #15.

Scores range from 1 (no fatigue) to 50 (severe fatigue). Do not assign a score to items #4-14 if respondent indicated they "do not do any activity for reasons other than fatigue". If respondents select no fatigue on item #1, assign a zero to items #2-16. Item #16 is not included in the GFI.

The change from baseline and percentage change from baseline in GFI at each visit will be calculated. Summary statistics for absolute values of GFI, change and percentage change from baseline will be tabulated by previous treatment group, visit, feeder study and overall DIUR-006 study.

Individual question scores and GFI will be listed.

EQ-5D™

The EQ-5D™ questionnaire consists of two parts, the EQ-5D™ descriptive system and the EQ visual analogue scale (VAS). The descriptive system consists of 5 dimensions: mobility, self-care, usual activities, pain/discomfort and anxiety/depression. The EQ VAS is a visual scale in which the subject gives a single score between 0 and 100.

The results from the dimensions will be combined using a standard method specially designed for the EQ-5D™ questionnaire to give a single index value (EuroQol Research Foundation). Two methods will be used to calculate the single index value:

Method 1 will use the directly elicited 5L value set for the EQ-5D[™] questionnaire as specified in Devlin 2016.

Method 2 will use mapping approach described in van Hout 2012.

A table showing the frequency and percent of subjects with each score for each of the domains will be produced by previous treatment group, visit and feeder study. The denominator for percentage calculations will be based on the number of subjects with an evaluable EQ-5D, at each scheduled visit. A shift table of baseline to end of study will be produced by domain, previous treatment group and feeder study. The denominator for percentage calculations will be based on the number of subjects with an evaluable EQ-5D, at each level of the pre-Chronocort® baseline assessment.

The change from baseline and percentage change from baseline will be calculated for both the single index value calculated from the 5 dimensions and the VAS score. Summary statistics for the absolute values of these two scores as well as change and percentage change from baseline will be tabulated by previous treatment group, visit and feeder study.

Individual question scores for the EQ-5D™ descriptive system, the calculated single index value and EQ VAS score will be listed.

14. Changes from the planned analyses

Due to the COVID-19 pandemic, subjects in the US may receive domiciliary visits to take blood samples for analysis of their 17-OHP and A4 levels. These samples are scheduled to be taken at baseline, Week 4, Week 12, Week 24 and 6-monthly visits at both 09:00 and 13:00 hours, but these domiciliary visits will only occur once daily (with a preference for 09:00 hours). As a result, at the time of finalising the SAP there will unavoidably be missing data from what is due to be collected.

Statistical Analysis Plan

Version: 6.0 12 July 2022

15. References

16.1. List of planned tables

16.1. List of planned tables		
Study population	TFL num.	Shell name
Subject disposition (All subjects)	14.1.1	DS200
Major and minor protocol deviations by high level category (All	14.1.2.1	DS201
subjects <interim analysis="" set="">)</interim>		
Major and minor COVID-19 related protocol deviations by high level	14.1.2.2	DS201A
category (All subjects <interim analysis="" set="">)</interim>	4442	D14200
Analysis sets (All subjects assigned to treatment)	14.1.3	DM200
Demographic characteristics (Full <interim> analysis set)</interim>	14.1.4	DM201
Baseline disease characteristics (Full <interim> analysis set)</interim>	14.1.5	DM202
CAH medical history (Full <interim> analysis set)</interim>	14.1.6.1	MH200
Other medical history excluding CAH related events (Full <interim> analysis set)</interim>	14.1.6.2	MH201
Prior medications (Full <interim> analysis set)</interim>	14.1.7.1	CM201
Concomitant medications excluding glucocorticoid steroids during study DIUR-006 (Full <interim> analysis set)</interim>	14.1.7.2	CM200
Duration of exposure (Full <interim> analysis set)</interim>	14.1.8.1.1	EX202
Duration of cumulative exposure (Full <interim> analysis set)</interim>	14.1.8.1.2	EX202A
Dose titration decisions (Full <interim> analysis set)</interim>	14.1.8.2	EX203
Dose increases, reductions and interruptions (Full <interim> analysis</interim>		EX204
set)	14.1.8.3	
Subject compliance (Full <interim> analysis set)</interim>	14.1.8.4	EX200
Disruptions due to COVID-19 pandemic (Full <interim> analysis set –</interim>	14.1.9	CV200
subset of subjects still in study at time of COVID-19 pandemic)		
Safety		
Table of adverse events in any category - subject level (Full <interim> analysis set)</interim>	14.3.1.1	AE220
Table of adverse events in any category - episode level (Full <interim> analysis set)</interim>	14.3.1.2	AE2201
All adverse events (Full <interim> analysis set)</interim>	14.3.1.3	AE200
Most common (>10% of subjects overall) adverse events (Full <interim> analysis set)</interim>	14.3.1.4	AE206
Adverse events by severity (Full <interim> analysis set)</interim>	14.3.1.5	AE205
Adverse events by outcome (Full <interim> analysis set)</interim>	14.3.1.6	AE204
Adverse events by action taken (Full <interim> analysis set)</interim>	14.3.1.7	AE203
Adverse events by causality (Full <interim> analysis set)</interim>	14.3.1.8	AE202
Repeat above 7 tables for SAEs		
Adverse events leading to discontinuation of study treatment (Full <interim> analysis set)</interim>	14.3.4.1	AE201
Listing of adverse events leading to discontinuation of study treatment (Full <interim> analysis set)</interim>	14.3.4.2	AE102
Serious adverse events leading to discontinuation of study treatment (Full <interim> analysis set)</interim>	14.3.4.3	AE2011

Listing of serious adverse events leading to discontinuation of study	14.3.4.4	AE1021
treatment (Full <interim> analysis set)</interim>	14.5.4.4	ALIUZI
Adverse events leading to use of sick day rules (Full <interim> analysis</interim>	14.3.5.1	AE208
set)		
Adverse events leading to use of sick day rules by sick day medication	14.3.5.1.1	AE2081
(Full <interim> analysis set)</interim>		
Adverse events leading to adrenal crises (Full <interim> analysis set)</interim>	14.3.5.2.1	AE209
Adrenal crises per 100 patient years (Full <interim> analysis set)</interim>	14.3.5.2.2	AE212
Adrenal crises per 100 patient years, excluding extreme cases (Full	14.3.5.2.3	AE213
<pre><interim> analysis set)</interim></pre>	14252	A F 2 4 4
Adverse events of unexpected therapeutic benefit (Full <interim> analysis set)</interim>	14.3.5.3	AE211
Signs and symptoms of adrenal insufficiency and over treatment (Full	14.3.6	FA200
<pre></pre>	1	
Repeat of AE Tables at episode level to be decided at Data Review		
meeting		
Haematology (1) laboratory variables (Full <interim> analysis set)</interim>	14.3.7.1.1	LB200
Change from pre-Chronocort baseline in Haematology (1) laboratory	14.3.7.1.2.1	LB201
variables (Full <interim> analysis set)</interim>	442742	152024
Shift table for Haematology (1) laboratory variables (Full <interim></interim>	14.3.7.1.3 14.3.7.1.4	LB202A LB202B
analysis set) Haematology (1) results considered clinically significant by the	14.3.7.1.4	LB202B LB203
investigator (Full <interim> analysis set)</interim>	14.5.7.1.5	LDZOS
Repeat above 4 tables for Haematology (2), Haematology (3)		
Biochemistry (1) laboratory variables (Full <interim> analysis set)</interim>	14.3.7.4.1	LB2003
Change from pre-Chronocort baseline in Biochemistry (1) laboratory	14.3.7.4.2.1	LB2013
variables (Full <interim> analysis set)</interim>		
Shift table for Biochemistry (1) laboratory variables (Full <interim></interim>	14.3.7.4.3	LB2023A
analysis set)	14.3.7.4.4	LB2023B
Biochemistry (1) results considered clinically significant by the	14.3.7.4.5	LB2033
investigator (Full <interim> analysis set) Repeat above 4 tables for Biochemistry (2), Biochemistry (3),</interim>		
Biochemistry (4)		
Vital signs variables (Full <interim> analysis set)</interim>	14.3.8.1.1	VS200
Vital signs variables, change from pre-Chronocort baseline (Full	14.3.8.1.2	VS201
<interim> analysis set)</interim>		
Vital signs shift table for SBP and DBP (Full <interim> analysis set)</interim>	14.3.8.1.4	VS203
	14.3.8.1.5	VS202
Abnormal findings in physical examination (Full <interim> analysis set)</interim>	14.3.8.1.6	PE200
Efficacy		
Total daily dose of Chronocort (Full <interim> analysis set)</interim>	14.2.1.1	EX205
Total daily dose of Chronocort, excluding extreme cases (Full	14.2.1.2	EX205A
<pre><interim> analysis set)</interim></pre>	44242	FV204
Total daily dose of Chronocort per body surface area (Full <interim></interim>	14.2.1.3	EX201
analysis set)		

Total daily dose of Chronocort distribution table (Full <interim> analysis set)</interim>	14.2.1.4	EX206
Disease control, 17-OHP at 09:00h (Full <interim> analysis set)</interim>	14.2.2.1.1	EF200
Disease control, 17-OHP at 09:00h, excluding extreme cases (Full <interim> analysis set)</interim>	14.2.2.1.2	EF200A
Disease control, 17-OHP at 09:00h by proportion of daily dose given at night (Full <interim> analysis set)</interim>	14.2.2.1.3	EF201
Disease control, 17-OHP at 13:00h (Full <interim> analysis set)</interim>	14.2.2.1.4	EF202
Disease control, 17-OHP at 13:00h, excluding extreme cases (Full <interim> analysis set)</interim>	14.2.2.1.5	EF202A
Disease control, 17-OHP at 13:00h by proportion of daily dose given at night (Full <interim> analysis set)</interim>	14.2.2.1.6	EF203
Subjects achieving <36.4 nmol/L for 17-OHP at 09:00 hours by visit (Full <interim> analysis set)</interim>	14.2.2.1.7	EF206
Repeat above 6 tables for A4 parameter		
Change from pre-Chronocort baseline in SDS at 09:00h (Full <interim> analysis set)</interim>	14.2.3.1.1	EF210
Change from pre-Chronocort baseline in SDS at 13:00h (Full <interim> analysis set)</interim>	14.2.3.1.2	EF211
Change from pre-Chronocort baseline of mean SDS over time (Full <interim> analysis set)</interim>	14.2.3.1.3	EF212
Absolute values of 17-OHP (nmol/L) over time (Full <interim> analysis set)</interim>	14.2.3.2.1.1	EF204
Absolute values of 17-OHP (nmol/L) over time, excluding extreme cases (Full <interim> analysis set)</interim>	14.2.3.2.1.2	EF204A
Change from pre-Chronocort baseline in 17-OHP (nmol/L) over time (Full <interim> analysis set)</interim>	14.2.3.2.2.1	EF205
Change from pre-Chronocort baseline in 17-OHP (nmol/L) over time, excluding extreme cases (Full <interim> analysis set)</interim>	14.2.3.2.2.2	EF205B
Change from Visit 1/Baseline in 17-OHP (nmol/L) over time (Full <interim> analysis set)</interim>	14.2.3.2.2.3	EF205A
Change from Visit 1/Baseline in 17-OHP (nmol/L) over time, excluding extreme cases (Full <interim> analysis set)</interim>	14.2.3.2.2.4	EF205C
Repeat above 6 tables for A4 parameter		
Summary of absolute values of body composition - Dual Energy X-ray Absorptiometry (Full <interim> analysis set)</interim>	14.2.4.1.1	VS204
Summary of absolute values of body composition excluding measurements post scanner change - Dual Energy X-ray Absorptiometry (Full <interim> analysis set)</interim>	14.2.4.1.2	VS2041
Summary of change from pre-Chronocort baseline in body composition - Dual Energy X-ray Absorptiometry (Full <interim> analysis set)</interim>	14.2.4.2.1	VS205
Summary of change from pre-Chronocort baseline in body composition excluding measurements post scanner change - Dual Energy X-ray Absorptiometry (Full <interim> analysis set)</interim>	14.2.4.2.2	VS2051
Change in Dual Energy X-ray Absorptiometry scanner results by site population (Full <interim> analysis set)</interim>	14.2.4.3	VS206

Summary of absolute values for bone markers and laboratory assessments of special interest (Full <interim> analysis set)</interim>	14.2.5.1	LB210
Summary of change from pre-Chronocort baseline for bone markers and laboratory assessments of special interest (Full <interim> analysis set)</interim>	14.2.5.2	LB211
Shift table of pre-Chronocort baseline to minimum on-treatment for bone markers and laboratory assessments of special interest (Full <interim> analysis set)</interim>	14.2.5.3	LB212
Shift table of pre-Chronocort baseline to maximum on-treatment for bone markers and laboratory assessments of special interest (Full <interim> analysis set)</interim>	14.2.5.4	LB2121
Summary of clinically significant results for bone markers and laboratory assessments of special interest (Full <interim> analysis set)</interim>	14.2.5.5	LB213
Summary of SF-36 scores (Full <interim> analysis set)</interim>	14.2.6.1.1	QS207
Summary of SF-36 change from pre-Chronocort baseline (Full <interim> analysis set)</interim>	14.2.6.1.2	QS208
Summary of SF-36 percentage change from pre-Chronocort baseline (Full <interim> analysis set)</interim>	14.2.6.1.3	QS209
Summary of GFI score derived from the MAF (Full <interim> analysis set)</interim>	14.2.6.2.1	QS204
Summary of GFI score derived from the MAF change from pre- Chronocort baseline (Full <interim> analysis set)</interim>	14.2.6.2.2	QS205
Summary of GFI score derived from the MAF percentage change from pre-Chronocort baseline (Full <interim> analysis set)</interim>	14.2.6.2.3	QS206
Summary of EQ-5D by domain (Full <interim> analysis set)</interim>	14.2.6.3.1	QS200
Shift table of baseline to end of study for EQ-5D by domain (Full <interim> analysis set)</interim>	14.2.6.3.2	QS210
Summary of EQ-5D absolute values (Full <interim> analysis set)</interim>	14.2.6.3.3	QS201
Summary of EQ-5D change from pre-Chronocort baseline (Full <interim> analysis set)</interim>	14.2.6.3.4	QS202
Summary of EQ-5D percentage change from pre-Chronocort baseline (Full <interim> analysis set)</interim>	14.2.6.3.5	QS203

Statistical Analysis Plan

Version: 6.0 12 July 2022

Protocol No.: DIUR-006

